Study Title: The Duration of Antibiotic Therapy for Early VAP (DATE) Trial

V. Inclusion and Exclusion Criteria

A) Inclusion Criteria

- a.** Surgical patient
- b.** Early VAP, defined as VAP occurring within 2 – 7 days of intubation (via endotracheal or tracheostomy tube) (9). VAP will be defined according to local institutional protocol.
- c.** Hospital length of stay (LOS) \leq 10 days at the time of VAP diagnosis.
- d.** Patients are willing to provide informed consent or their Legally Authorized Representative (LAR) is willing to provide informed consent on their behalf when the patient is unable (i.e., cognitively impaired from sedation on a ventilator).

B) Exclusion Criteria

- a.** Age $<$ 18 years
- b.** Prior episode of VAP for the index admission
- c.** VAP caused by any of the following pathogens:
 - i.** Methicillin-resistant *Staphylococcus aureus* (MRSA)
 - ii.** Vancomycin-intermediate *Staphylococcus aureus* (VISA)
 - iii.** *Pseudomonas aeruginosa*
 - iv.** Vancomycin-resistant *Enterococcus* (VRE)
 - v.** *Acinetobacter baumanii*
 - vi.** *Stenotrophomonas maltophilia*
 - vii.** Carbapenem-resistant *Enterobacteriaceae* (CRE)
 - viii.** Extended-spectrum beta lactamase-producing gram-negative bacilli
- d.** Causative pathogen not sensitive to choice of initial empiric antibiotic
- e.** Antibiotic therapy for \geq 5 of the last 10 days preceding VAP diagnosis
- f.** Septic shock, defined as evidence of tissue hypoperfusion after adequate volume expansion, due to infection, and requiring \geq 1 vasopressor (17)

UM IRB No.: 20211211

NCT05545735

Protocol Date: November 14, 2023

Principal Investigator: [name]., M.S.P.H.

Study Title: The Duration of Antibiotic Therapy for Early VAP (DATE) Trial

- g.** Current or recent (within 30 days) use of immunosuppressive medications
- h.** LOS \geq 72 hours at a transferring facility
- i.** Pregnancy or lactation
- j.** Legal arrest or incarceration
- k.** Moribund state in which death is imminent
- l.** ECMO (Extracorporeal membrane oxygenation)
- m.** Extubation prior to randomization

VI. Number of Subjects

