The total required sample size for this study is **458 patients**. Assumptions for the power analysis include non-inferiority for VAP recurrence and superiority for antibiotic-free days in the intervention group, 3 planned analyses of the data with O'Brien-Fleming spending function with binding futility boundaries, 25% recurrence rate in the control group (14), and 6 enrolling centers with an average cluster size of 10. To detect a 10% difference in outcomes between groups with 80% power and assuming a 10% dropout rate, a total sample size of 458 patients is required for this study. Sample size will be recalculated at each interim analysis with better estimates based on accrued patients. The planned analyses will take place after enrollment of 150, 300, and all patients.

VII. Study-Wide Recruitment Methods

This is a multicenter randomized controlled trial. We have partnered with the Surgical Infection Society to aid in recruitment of interested centers for participation in the study. The recruitment methods for individual subjects to participate in the study will be uniform across all centers. A member of the research team at each center will screen all patients in their respective surgical ICUs by reviewing the medical record of each patient in the ICU for eligibility based on the inclusion and exclusion criteria listed in *Section V* (above). Screening will occur daily during the study period. We will be requesting a waiver of the requirement for written authorization

UM IRB No.: 20211211

NCT05545735

Protocol Date: November 14, 2023

Principal Investigator: [name]., M.S.P.H.

Study Title: The Duration of Antibiotic Therapy for Early VAP (DATE) Trial

from patients to access their health records due to the nature of the study. Please see further documentation in *Section XXXII* (below).

VIII. Study Timeline

Each individual patient enrolled in the study will be followed for 30 days or until hospital discharge, whichever occurs first. We will also review patient charts at hospital discharge to determine overall hospital length of stay and overall mortality, in addition to 30-day outcomes. We expect all subjects to be enrolled within the first 2 years of study across all centers, with full data analysis completed at 3 months after study completion.

IX. Study Endpoints

A) Primary Outcomes

- a.** VAP recurrence within 30 days
 - i.** VAP recurrence = VAP occurring 2 – 14 days following completion of initial therapy

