- b.** Antibiotic-free days within 30 days

B) Secondary Outcomes

- a.** Antibiotic exposure
 - i.** Days of antibiotics
 - ii.** Antibiotic days (defined as the product of days of antibiotics and number of antibiotics per day)
- b.** Clinical improvement, measured using daily CPIS_{clinical} score while enrolled in the study
- c.** VAP relapse = recurrent VAP caused by initial pathogen (if culture data available), occurring 2 – 14 days following completion of initial therapy
- d.** 30-day Ventilator-free days

UM IRB No.: 20211211

NCT05545735

Protocol Date: November 14, 2023

Principal Investigator: [name]., M.S.P.H.

Study Title: The Duration of Antibiotic Therapy for Early VAP (DATE) Trial

- e. Empyema
- f. Need for tracheostomy
- g. Non-pulmonary infections
- h. 30-day ICU-free days
- i. Hospital LOS
- j. In-hospital Mortality

X. Procedures Involved

This is a multicenter, randomized, clinical trial. The trial will be reported in accordance with the recommendations of the CONSORT statement (18). IRB approval will be obtained. All subjects, or their legally authorized representatives, will provide written consent for study participation. The trial is registered with the US National Institutes of Health (ClinicalTrials.gov Identifier #NCT05545735).

Screening will occur daily by study personnel. Eligible patients will be approached as soon as possible after inclusion criteria are met (i.e., 1 – 3 days prior to randomization). Randomization will occur using a computer-generated block pattern no later than the end of the fourth day of appropriate antibiotic therapy. Randomization will occur at the hospital level in blocks of 20.

Empiric antibiotic therapy will be instituted as soon as possible following diagnosis of suspected pneumonia by the clinical team. The default antibiotic will be based on the local institutional antibiogram and practice. Pre-existing treatment for a non-pulmonary infection with at least one antibiotic that has appropriate activity against the VAP pathogen may be substituted for the default antibiotic. Once sensitivity data become available, therapy may be de-escalated to a more narrow-spectrum agent, as indicated.

The default duration of antibiotic therapy will be determined by study group assignment; the treatment team will be asked to adhere to study group assignment whenever possible. However, the treatment team may choose to extend the duration of antibiotic therapy based on

UM IRB No.: 20211211

NCT05545735

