This is a multicenter randomized controlled trial. The University of Miami will serve as the coordinating center for the study and [name], Assistant Professor of Surgery in the Divisions of Trauma and Surgical Critical Care, DeWitt Daughtry Family Department of Surgery, University of Miami Miller School of Medicine, will serve as the lead investigator. [name], ARNP, MSPH, will serve as the study coordinator.

Prior to enrollment of the first study participant, we will coordinate a meeting of all site PIs and coordinators to review the study protocol and answer any questions. This meeting will occur via a virtual meeting platform (e.g., Zoom). During this meeting, we will ensure that all sites have the current protocol. We will also ensure that all appropriate safeguards are in place, including a location for CRFs to be stored in a locked office. Prior to this meeting, we will ensure that all sites have received IRB approval from their local IRB. We will plan to meet with all sites via virtual meeting platform from 1 – 4 times per month, as appropriate, at which time we will ensure study compliance, timely reporting of adverse events, and answer additional questions. Prior to the implementation of any study modification, we will contact all sites, ensure that the modification has been submitted to their local IRBs, and ensure that approval has been attained from their local IRBs. DSMB reports will be furnished to each site via either email or during one of these study meetings. Any problems with the study and closure of the study will also be reported as outlined above.

XIX. Community-Based Participatory Research

This study does not involve community-based participatory research.

UM IRB No.: 20211211

NCT05545735

Protocol Date: November 14, 2023

Principal Investigator: [name]., M.S.P.H.

Study Title: The Duration of Antibiotic Therapy for Early VAP (DATE) Trial

XX. Sharing of Results with Subjects

Results of the study will not be shared with individual subjects. The findings of the study will be presented at the Annual Scientific Meeting of the Surgical Infection Society and published in a peer-reviewed journal upon study completion.

XXI. Setting

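### One fixed block of 20 per hospital, printed in the protocol every site holds, lets a site that tallies its own assignments deduce up to about 9% of them (about 7% over the six stated centers)

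*Combined protocol and SAP*

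**What the plan says.** - **Block size.** Section X (Procedures Involved) and Section XII (Data Management) carry the same sentence: "Randomization will occur at the hospital level in blocks of 20". Since patients consent and are randomized individually, I read this as stratification by hospital.
- **Method.** Section X adds only that "Randomization will occur using a computer-generated block pattern". The allocation ratio, the custodian of the list and the way an assignment is released are not described in the text available to me.
- **Who holds the block size.** Section XVIII (Multi-Site Research) says of the start-up meeting that "we will ensure that all sites have the current protocol".
- **Who sees assignments.** No masking is described. Section X says "the treatment team will be asked to adhere to study group assignment whenever possible", so the treating team must know the arm.
- **Timing.** Section X states: "Eligible patients will be approached as soon as possible after inclusion criteria are met (i.e., 1 – 3 days prior to randomization". Randomization itself is due "no later than the end of the fourth day of appropriate antibiotic therapy". Section V.B lists "Extubation prior to randomization" as an exclusion (item m).
- **Size of the trial.** Section VI states that "a total sample size of 458 patients is required for this study", and assumes six centers and an average cluster size of 10.

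**The concern.** Blocking forces the arms to balance at the end of each block. If the block length is fixed and known, and past assignments are visible, then once one arm has used all its places every remaining assignment in that block is certain. Before that, the arm that is behind is the better guess.

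Prediction matters only if someone can act on it before the patient is randomized. Here the approach precedes randomization by up to three days, the time of randomization is flexible, and a patient extubated in the interval leaves the trial. A site that knew the next arm would therefore have room to hurry or delay a patient. The people randomized to each arm could then differ systematically. Intention-to-treat analysis keeps randomized patients in their assigned arm, but it cannot restore patients who were never randomized. The model adjustment in Section XII reaches measured baseline variables only.

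**Working it through.** The plan gives no predictability figure, so there is none to reproduce. The total of 458 is taken as stated.

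**Inputs.** Block of 20 within hospital (Sections X, XII); 458 patients, six centers, average cluster size 10 (Section VI). Assumption: 1:1 allocation, so 10 places per arm in each block.

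**Step 1: certainty by position.** In a 1:1 block of 2m, assignment j is certain if one arm is already full: P(j) = 2·C(j−1, m)/C(2m, m). For m = 10, C(20,10) = 184,756.

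| Position in block | P(certain) |
|---|---|
| 1 to 10 | 0 |
| 11 to 14 | at most 0.3% each |
| 15 | 1.1% |
| 16 | 3.2% to 3.3% (0.0325) |
| 17 | 8.7% |
| 18 | 21.1% |
| 19 | 47.4% |
| 20 | 100% |

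**Step 2: complete block.** The sum is 2m/(m+1) = 20/11 = 1.82 certain assignments per block, a share of 1/(m+1) = 1/11 = 9.1%. If every patient fell in a complete block, that would be 458/11 = 41.6 patients.

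**Step 3: the plan's own site numbers.** An even split of 458 over six centers gives four sites of 76 and two of 77 (4 × 76 + 2 × 77 = 458).

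- Site of 76: three complete blocks plus 16 places = 3 × 1.818 + 0.047 = 5.502.
- Site of 77: three complete blocks plus 17 places = 3 × 1.818 + 0.134 = 5.589.
- Total: 4 × 5.502 + 2 × 5.589 = 33.2, and 33.2/458 = 7.2%.

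At 10 patients per site no block passes its tenth place, so the figure is 0%. The two assumptions in Section VI do not fit together: 6 × 10 = 60, and 458 patients at 10 per site would need about 46 sites. Intermediate site sizes give 6.1% (30 patients) and 7.3% (50 patients).

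**Step 4: guessing.** A site that always guesses the arm that is behind is right, over a complete block of 2b, in a share [b + (4^b/C(2b,b) − 1)/2]/(2b) of cases.

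- b = 10: [10 + (5.676 − 1)/2]/20 = 61.7%
- b = 8: [8 + (5.092 − 1)/2]/16 = 62.8%
- b = 6: [6 + (4.433 − 1)/2]/12 = 64.3%

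Chance is 50%. At 76 per site with blocks of 20 the rate is about 61%; at 10 per site it is about 55%.

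**Step 5: does varying the size help by itself?** Take sizes 12, 16 and 20 with equal probability, and suppose that sites know this set and where each block starts. An assignment is then certain only when one arm has reached 10, which requires a block of 20. The share is (1/3 × 20/11)/16 = 3.8%, against 9.1%. The best-guess rate, however, rises to about 62.7%, against 61.7%, because the average block is shorter. Varying the size thus removes much of the certainty but does not reduce guessing. The protection comes from withholding the sizes and from keeping blocks long.

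**The case against.** **Twenty is already a long block.** This is correct. Fixed blocks of 4, 6 or 10 would give 33%, 25% or 17% certain assignments. Length is not the weakness; the weakness is a single size disclosed to sites.

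**Deduction takes effort, and it bites late in the block.** Someone must record every assignment at the hospital and know where each block began, and certainty is rare before position 17. This stands: the percentages are what a site could deduce, not what sites will know. Still, the tally needs only the site's own visible assignments, and concealment should not depend on nobody counting.

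**A reader might infer that sites may decline to randomize a consented, eligible patient.** No section says so. Extubation is a clinical event, not a discretionary exclusion. The room to act is inferred from the interval after approach and the flexible timing. That the trial is open-label is likewise inferred, though fairly.

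**A reader might infer a bias toward non-inferiority,** with sicker patients kept out of a certain 4-day place. The documents do not support a direction. Sections X and XIV put clinical decisions above the assignment, so a worried clinician can extend treatment and has less reason to interfere with enrollment. No effect on the recurrence difference or on type I error can be derived from the plan.

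**Concealment may be described elsewhere.** Some of the protocol, including text following the Section XXI heading, was not available to me. The point therefore rests on the disclosed fixed size, not on a claim that no concealment procedure exists.

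**Conclusion.** The concern holds in a limited form. The protocol gives sites the one fact, a fixed block size, that turns their visible past assignments into knowledge of some future ones. The amount is at most about 9% in complete blocks, about 7% (33 of 458) over six equal centers, and zero at 10 per site. A flat figure of 42 patients known in advance is not supported, because it needs every block at every site to be completed and every site to keep count.

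The result assumes 1:1 allocation, stratification by hospital, assignments visible to the site, and a known start of each block. It establishes an opportunity for selective enrollment, not that selection will occur, nor how large a bias would be or which way it would run. It is worth correcting because the correction is inexpensive and no analysis can make good the damage afterward.

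**What to change.** For future patients, replace the block statement in Sections X and XII with wording such as: *stratified by hospital, in permuted blocks of randomly varying size, with the sizes held in a document not given to sites and each assignment released centrally only after the patient is irrevocably enrolled.* State the allocation ratio in the same place.

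Keep the blocks long, since shorter ones raise the guess rate (Step 4). Start a new list instead of finishing blocks now open, because sites already know that those hold 20 places. Some advantage from guessing the arm that is behind remains under any blocked scheme; the change is aimed at assignments that can be deduced with certainty.

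The cost is a new allocation list, a short amendment and slightly less exact balance between arms at any moment.

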Protocol Date: November 14, 2023

Principal Investigator: [name]., M.S.P.H.

Study Title: The Duration of Antibiotic Therapy for Early VAP (DATE) Trial

clinical circumstances, such as deterioration in hemodynamic or respiratory status that is believed to be related to incompletely treated VAP, or continued treatment of a non-pulmonary infection. The treatment team may also decide to extend the duration of antibiotic therapy based on the results of procalcitonin measurements, if obtained. Clinical decisions will take precedence over study group assignment.

Patients will be followed for 30 days or until hospital discharge, whichever occurs first. Please see the attached data collection tool for detailed information.

Adverse event monitoring will occur daily at each individual institution. Any adverse event will trigger notification to the site PI per local IRB regulations. The safety of the study will be monitored by an independent Data Safety Monitoring Board (DSMB). The DSMB has been formed by the Surgical Infection Society and will consist of Drs. [name], [name], and [name]. The committee will meet after each planned interim analysis (see *Sections VI and XII*) and submit a written report to the overall study PI ([name]), who will submit to the IRB (see attached “*DSMB Charter*”).

Disease Related Adverse Events: It is recognized that this patient population who require critical care support will experience a number of common aberrations in laboratory values, signs, and symptoms due to the severity of the underlying disease and the impact of standard therapies. These will not necessarily constitute an AE unless they:

- require significant intervention,
- lead to discontinuation of study procedures,
- felt to be related to study procedures
- or are considered to be of concern, in the Investigator’s clinical judgment.

Examples of the type of AEs that may be associated with the patient population are acute respiratory failure; respiratory distress; acute lung injury; acute respiratory distress syndrome (ARDS); acute renal failure; fever, bacteremia; sepsis, septic shock; hypotension; metabolic acidosis, pleural effusion; mineral or electrolyte imbalance. For purposes of this study, deaths

UM IRB No.: 20211211

NCT05545735

Protocol Date: November 14, 2023

Principal Investigator: [name]., M.S.P.H.

Study Title: The Duration of Antibiotic Therapy for Early VAP (DATE) Trial

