will be captured as clinical outcomes and do not need to be reported as SAEs unless felt related to study procedures.

XI. Data and Specimen Banking

There will be no specimen banking for this study.

XII. Data Management

All data will be collected on the attached case report form (CRF) and then input by study personnel at each individual site into the University of Miami REDCap electronic data management system. Each site PI will be responsible for keeping a secure file linking the patient medical record number (MRN) to their study ID in the event that additional information is required for study analysis, which will be destroyed at the conclusion of the study. All data will be entered into REDCap in a de-identified manner, using only the study ID, without including any personal identifying information. Data analysis will be performed by [name], PhD. [name] is a tenured Professor of Surgery and Public Health at the University of Colorado Denver and the Colorado School of Public Health, where she is also the Associate Director of the NIH-funded T32 postdoctoral research fellowship in trauma surgery, and statistical consultant to the Ernest E. Moore Shock Trauma Center at Denver Health Medical Center. Additionally, she is the former Statistical Editor for the *Journal of Trauma and Acute Care Surgery*, with over 30 years' experience in injury-related research, particularly in critically ill and injured patients.

Three equally spaced analyses (two interim and one final) will be conducted for all outcomes, using the O'Brien-Fleming alpha spending function. Data analyses will be performed using SAS v9.4 (SAS Inc., Cary, NC). Randomization will occur at the hospital level in blocks of 20. Data will be analyzed using an intention-to-treat strategy (i.e., data of patients randomized to receive 4 days of antibiotic therapy will be analyzed as belonging to this group even if they receive longer courses) and a per-protocol strategy (i.e., crossovers and protocol violations

UM IRB No.: 20211211

NCT05545735

Protocol Date: November 14, 2023

Principal Investigator: [name]., M.S.P.H.

Study Title: The Duration of Antibiotic Therapy for Early VAP (DATE) Trial

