excluded). Data will be expressed as median (interquartile range) or frequency (%). Normality of continuous variables will be assessed by visual inspection of histograms. Differences in the means of continuous normally distributed variables will be assessed using Student's t-test or ANOVA. Differences in the medians of non-normally distributed continuous variables will be assessed using the Wilcoxon rank sum or Kruskal-Wallis tests. Proportions will be compared using the chi-squared or Fischer's exact test, as appropriate. Univariate analysis of categorical outcomes will be expressed as the relative risk with 95% confidence intervals, with standard errors adjusted for intra-center clustering. A generalized estimating equation or linear mixed model (with appropriate transformation of outcome variables to approximate normality, if needed) will be fit to address possible confounding if randomization fails to assure equitable distribution. Baseline variables associated with randomization status at the $p < 0.25$ level by univariate analysis will be added to the model using a stepwise selection method. The overall contribution of the fitted model to predicting variability in the outcome of interest will be assessed using the likelihood ratio chi-squared test. The alpha error level is defined at 0.05, with statistical significance at $p < 0.05$. No adjustment for multiplicity of outcomes will be done as this is an exploratory (rather than confirmatory) trial, and all hypotheses are pre-planned. Adjustment for multiple comparisons in pre-planned hypotheses leads to more type II errors (19, 20).

XIII. Provisions to Monitor the Data to Ensure the Safety of Subjects

As mentioned previously (see *Section X*), a DSMB will be convened. The DSMB will meet after each planned interim analysis, review data collected across all sites, and submit a written report to the overall study PI, who will submit the report to the IRB. Data analysis will be performed by [name], as mentioned above (see *Section XII*).

Data will be monitored daily at each site and any adverse events will be reported to the site PI per local IRB regulations. Efficacy and safety data will be collected on CRFs and inputted into REDCap by study personnel at each site. The study will be terminated early if there are

UM IRB No.: 20211211

NCT05545735

Protocol Date: November 14, 2023

Principal Investigator: [name]., M.S.P.H.

Study Title: The Duration of Antibiotic Therapy for Early VAP (DATE) Trial

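### A concurrent non-pulmonary antibiotic course planned past day 4 shrinks or removes the 4- versus 7-day contrast, and the per-protocol rule does not repair it; flag these patients before randomization

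*Combined protocol and SAP*

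**What the plan says.** Protocol section X (Procedures Involved) expects these patients: "Pre-existing treatment for a non-pulmonary infection with at least one antibiotic that has appropriate activity against the VAP pathogen may be substituted" for the default VAP antibiotic. The same section lets the team lengthen treatment for deterioration "believed to be related to incompletely treated VAP, or continued treatment of a non-pulmonary infection", sets no limit on the extension, and adds: "Clinical decisions will take precedence over study group assignment". Randomization may wait until the end of the fourth day of appropriate therapy.

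In section V, the only criterion based on how long antibiotics have been given is exclusion e, and it looks back: antibiotics on 5 or more "of the last 10 days preceding VAP diagnosis". Nothing there concerns how long another course still has to run.

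Section XII (Data Management) plans two analyses. Under ITT, "data of patients randomized to receive 4 days of antibiotic therapy will be analyzed as belonging to this group even if they receive longer courses". The other is "a per-protocol strategy (i.e., crossovers and protocol violations" excluded). Neither crossover nor violation is defined, so the text does not say whether a permitted extension counts as one. A covariate model may add "Baseline variables associated with randomization status at the" p < 0.25 level. The case report form is attached to the protocol but is not part of the public text.

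**The concern.** The trial tests whether stopping at day 4 instead of day 7 raises VAP recurrence. A patient with an active course for another infection that must continue past day 4 cannot stop active therapy at day 4, whatever the assignment. This trait is present before randomization; it is not poor adherence. Extensions for clinical deterioration are a different matter and are not part of this point.

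In a non-inferiority comparison, lost contrast pulls the arms together. The usual counterweight is the per-protocol analysis, and here it fails under either reading of its rule:

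- If a permitted extension is not a violation, the patients without contrast stay in per-protocol as well.
- If it is a violation, some of them leave one arm and stay in the other, so a baseline trait decides who is analyzed in one arm only.

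The covariate model does not help. It selects variables by imbalance between arms, and adjustment cannot restore a contrast that was never delivered.

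**Working it through.** **Inputs from the protocol.** Section VI gives 458 patients and a 25% control recurrence rate, and states the target as "To detect a 10% difference in outcomes between groups with 80% power and assuming a 10% dropout rate". The 10% is read here as the non-inferiority margin, although the text does not call it one. Section XII gives alpha 0.05 without saying one- or two-sided, so both one-sided levels are shown.

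**The plan's own figure.** The stated inputs do not reproduce 458. At 25% in both arms, a 10-point margin, 80% power and one-sided 0.05, the total is 464, or 464/0.9 = 516 after dropout, before interim looks and clustering. That is a separate matter. Here 458 is taken as given, which leaves 458 × 0.9 / 2 = 206 evaluable per arm.

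**Step 1: contrast per patient.** Let L be the days of active non-pulmonary therapy still planned at VAP diagnosis. Treatment lasts max(4, L) days in the short arm and max(7, L) in the long arm. Let C be an assumed planned course, with k = 1 to 4 days already given (5 or more would trigger exclusion e), so L = C − k.

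| C | L for k = 1, 2, 3, 4 | Contrast (days) |
|---|---|---|
| 7 | 6, 5, 4, 3 | 1, 2, 3, 3 |
| 10 | 9, 8, 7, 6 | 0, 0, 0, 1 |
| 14 | 13, 12, 11, 10 | 0, 0, 0, 0 |

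**Step 2: ITT on recurrence.** Suppose 4 days is worse by exactly 10 points (35% versus 25%) where the arm controls duration, and a share s has no contrast (L of 7 or more). The ITT difference is 10 × (1 − s) points. The chance of declaring non-inferiority is the exact binomial probability that the upper Wald limit lies below 10 points, with 206 per arm, a single look and no clustering.

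| s (assumed) | ITT difference (points) | One-sided 0.025 | One-sided 0.05 |
|---|---|---|---|
| 0 | 10 | 2.5% | 5.0% |
| 5% | 9.5 | 3.3% | 6.3% |
| 10% | 9 | 4.2% | 7.8% |
| 20% | 8 | 6.6% | 11.7% |
| 30% | 7 | 10.0% | 16.7% |

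Hand check at s = 10%: SE = √[(0.34 × 0.66 + 0.25 × 0.75)/206] = 0.0447. Then (0.10 − 0.09)/0.0447 − 1.96 = −1.74, which gives about 4.1%.

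**Step 3: ITT on antibiotic-free days.** A 3-day contrast becomes 3 × (1 − s): 2.7, 2.4 and 2.1 days at s = 10, 20 and 30%. This works against the superiority claim.

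**Step 4: per-protocol, if a permitted extension counts as a violation.** Patients with L = 5 to 7 exceed a 4-day assignment but fit a 7-day one, so they leave the short arm only. Patients with L of 8 or more exceed both assignments and leave both arms. In the table, 10 of 12 cells run past day 4, and 4 of those 10 have L = 5 to 7.

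As an illustration, assume no true effect, 20% of patients with a course past day 4, and a recurrence risk of 35% in them against 25% overall. Weighting the 10 cells equally, 8% leave the short arm only and 12% leave both arms.

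- Short arm: (0.25 − 0.20 × 0.35)/0.80 = 22.5%.
- Long arm: (0.25 − 0.12 × 0.35)/0.88 = 23.6%.
- Bias: −1.1 points, toward non-inferiority.

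If all 20% had L = 5 to 7, the bias would be 22.5 − 25 = −2.5 points. With a risk of 15% instead of 35%, that extreme becomes (0.25 − 0.20 × 0.15)/0.80 − 0.25 = +2.5 points. The direction is therefore not fixed.

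**The case against.** The strongest reply concerns the estimand. The protocol assigns a default duration and openly permits extension, so ITT estimates the effect of that policy in everyone eligible. On that target, a true difference of 7 to 9 points lies inside a 10-point margin, and declaring non-inferiority is not an error. This stands. The probabilities above are errors only relative to the effect in patients whose duration the arm controls. It is a good reason to leave the primary ITT analysis alone. It does not rescue per-protocol, whose purpose is to describe the contrast actually delivered.

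Two stronger readings are tempting. A reader might infer that assignment has no influence on duration in any of these patients, and that per-protocol loses them all from the 4-day arm. The documents do not support this: courses with 5 or 6 days left keep 1 or 2 days of contrast, and one-sided loss is confined to 5 to 7 days left, under one of two readings of an undefined rule. A reader might also add the ITT dilution to the 2.5-point per-protocol shift. The no-contrast group and the one-sided group overlap only at exactly 7 days left, so the two worst cases largely cannot occur together.

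It is also fair that every share and risk shift here is assumed, that the other exclusions and the 10-day limit on hospital stay reduce the pool by an unknown amount, and that the unseen case report form may already record concurrent therapy. A form field alone would not change the analysis rules.

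**Conclusion.** The concern holds in a limited form. The protocol admits patients whose other antibiotic course shrinks or removes the treatment contrast, and neither planned analysis handles them cleanly. ITT dilution favors non-inferiority on recurrence only if 4 days is truly worse, and it weakens the antibiotic-free-days claim. Per-protocol is either diluted too or biased in a direction that cannot be predicted.

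The size depends on a share that the documents do not give. At an assumed 5 to 30% without contrast, the chance of declaring non-inferiority at a true 10-point excess rises from 2.5% to 3.3–10.0% at one-sided 0.025. This takes the stated 10% as the margin and ignores interim looks and clustering.

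A reader might infer that these patients must be excluded from the trial. The documents do not support that as a required correction, because a policy of default durations with permitted extension is a legitimate object of study. This is an inexpensive improvement to the analysis plan.

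**What to change.** Record a yes/no flag before randomization: is a non-pulmonary course with an agent active against the VAP pathogen planned beyond day 4 of VAP therapy? Take it from existing orders. Randomization can wait until the end of day 4, so the plan should usually be known by then. For patients already randomized, set the flag retrospectively, using only orders dated before randomization so that the assigned arm cannot influence it.

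Then:

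- keep the primary ITT analysis as planned;
- remove flagged patients from both arms in per-protocol;
- add an ITT sensitivity analysis without flagged patients;
- keep the permission to extend treatment, unchanged.

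The cost is one field, an amendment through the local IRBs, and a smaller per-protocol set. The flag does not settle how to treat extensions for infections that arise after randomization; that still needs its own definition.

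Excluding flagged patients from future enrollment is an option for the sponsor. Applied from the start, it would require 458/(1 − s) otherwise-eligible patients, with s now the flagged share: about 483, 509, 573 or 655 at 5, 10, 20 or 30%. It would slow enrollment and narrow the population, and it would remove patients with 5 or 6 days left who still carry some contrast.
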